Four patients with PAD (Age: 66.0 ± 10.9 years; Body Mass: 84.3 ± 17.1 kg) completed pilot testing of initial and maximum claudication distances while walking with and without an AFO. Patients completed a progressive-load treadmill test⁶⁷. During the treadmill test, the patients with PAD walked on a treadmill that started at 0% grade and 0.83m/sec. Every two minutes, the grade was increased by 2% up to a maximum of 15% grade. The first indication of claudication pain was recorded as initial claudication distance, while the total distance the patients could walk on the treadmill before stopping because of pain was the absolute claudication distance⁶⁷. Throughout the test, we asked the patient to confirm the presence or absence of pain to ensure the

correct initial claudication distance was recorded. We counterbalanced the effect of the AFO by having two patients walk first with the AFO, while the other two walked first without the AFO to prevent a fatigue effect. On average, the patients' initial claudication distance was 140.1 ± 72.5 meters while walking without the AFO and 183.5 ± 121.2 meters while walking with the AFO (Figure 9). The average maximum claudication distance was 366.0 ± 118.3 meters without the AFO and 492.3 ± 66.8 meters with the AFO (Figure 10). Thus, the four patients increased the maximum distance walked by about 50 meters just by wearing the AFO. These increases in initial and maximum walking distances are comparable to those seen after pharmacotherapy for six months^{29, 32}.

[figure not shown]

Figure 9. Initial claudication distances improve while walking with an ankle foot orthosis (AFO) compared to walking without an AFO in patients with PAD.

[figure not shown]

Figure 10. Maximum claudication distances are increased in patients with peripheral arterial disease when walking with an ankle foot orthosis (AFO).

Wearing an AFO trends towards redistribution of torque to the hip in patients with PAD. Four patients with PAD (Age: 60.3 ± 7.21 years; Body Mass: 82.6 ± 18.05 kg) were tested while walking overground with and without the AFO. Peak torque was calculated for the ankle at the end of the stance phase and hip extensor torque was calculated from early stance in each condition.

The preliminary results show that the ankle plantarflexor muscles have to contribute less torque to walking while

[figure not shown]

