Approach: We propose to study 50 patients with PAD, measuring walking performance with and without wearing a carbon composite AFO. Patients will wear the AFO on the affected leg(s), so patients with bilateral leg symptoms will wear them on both legs while patients with unilateral disease will wear the AFO on the symptomatic leg only. Walking performance will include measurement of initial and absolute walking distances, and lower extremity torque and power. Energy cost and muscle activity will be tested as potential mechanisms contributing to improvement in walking performance. Conditions will be randomized, with half of the subjects performing the tests without the AFO and the other half starting with the AFO walking conditions. All data will be collected in the Biomechanics Research Building (BRB). All subjects will be consented after reporting to the BRB and the outcomes detailed below will be assessed. The entire process is expected to take 2.5 hours.

Outcomes

- 1) **Initial and absolute walking distances:** Walking distances will be determined with a progressive-load treadmill test⁶⁷ with initial and maximum claudication distances as outcomes. During the treadmill test, patients will walk on a treadmill that starts at 0% grade and 2.0 mph. Every two minutes, the grade will be increased by 2% up to a maximum of 15% grade, and the speed held constant throughout the test⁶⁷.
- 2) **Lower extremity torque and power:** Biomechanical data will be collected using eight in-ground AMTI force platforms and a 12 camera high speed digital motion capture system (Cortex 5.1, Motion Analysis Corp, Santa Rosa, CA) to collect three dimensional kinematics (60 Hz) and kinetics (ground reaction forces, 600 Hz). Reflective markers will be placed at specific anatomical locations on the lower limbs, utilizing the marker systems of Vaughan⁷⁰ and Nigg⁷¹. Following the setup, kinematics and ground reaction forces will be recorded while the subjects walk with their self-selected pace through a ten-meter pathway. Each patient will be tested before the onset of claudication pain (pain free) with a mandatory one-minute rest period between the walking trials to insure that all trials are in a pain free condition. A total of five walking trials per leg will be collected. Following the collection of overground data, the patients with PAD will be allowed to rest.

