electromyographic signal provides a window into muscle fatigue and motor unit recruitment⁷³. The raw electromyographic signal will be converted to the frequency domain using a Fast Fourier Transform to determine the power spectrum. Median frequency and frequency bandwidth will be computed from the power spectrum. Median frequency will be computed as the frequency at half of the integrated power spectrum as given by the following equation (1)⁷³:

$$(1) \int_0^{f_{med}} P(f)df = \int_{f_{med}}^{f_{max}} P(f)df \int_0^{f_{med}} P(f)df = \int_{f_{med}}^{f_{max}} P(f)df$$

where $P(f)$ is the power at frequency f , f_{med} is the median frequency, and f_{max} is the maximum frequency of the power spectrum. Frequency bandwidth (f_{band}) is the difference between the highest and lowest frequency where the power exceeds half the maximum power of the power spectrum.

4) **Energy cost:** A portable metabolic cart (Cosmed K4b2, Cosmed USA Inc., Chicago, IL), will be used to measure gas exchange on a breath-by-breath basis, providing a measure of oxygen consumption. Steady-state oxygen consumption in ml/kg/min will be calculated during the walking distance test.

Statistical analysis: The sample size was calculated to detect effect sizes observed in pilot data for initial and absolute walking distances. The mean (SD) difference in initial walking distance with and without AFO was 43.4 meters (93), corresponding to a standardized effect size of 0.47 standard deviations. A sample size of 50 subjects will provide 84% power to detect differences of 0.47 standard deviations between walking with and without an AFO, using a paired t-test for sample size estimation purposes only, and a significance level of 0.02 to informally adjust for multiple testing. The standardized effect size for absolute walking distance was 1.29 standard deviations, so the sample size of 50 subjects will also provide sufficient power to detect this difference. For statistical analysis, a linear (or generalized linear, as appropriate) mixed modeling approach will be used. This approach will allow us to detect differences between walking with and without an AFO while adjusting for confounding variables. The level of significance will be set at 0.05.

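### Aim 1 randomises the order of the two walking conditions but names no test-order term in the analysis, so any shift between first and second test is counted as error; adding the term is a nearly free improvement.

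*Combined protocol and SAP*

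**What the plan says.** The Approach paragraph of Specific Aim 1 (section 4) has 50 patients tested with and without the AFO: "Conditions will be randomized, with half of the subjects performing the tests without the AFO", and the other half starting with it. The whole process is expected to take 2.5 hours. Rest is mentioned after the overground trials. No rest between the two treadmill tests is stated.

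The pilot subsection of section 4 used the same kind of progressive treadmill test in four patients. Two walked first with the device, "while the other two walked first without the AFO to prevent a fatigue effect".

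The Statistical analysis paragraph of Aim 1 sizes the study with a paired t-test: "A sample size of 50 subjects will provide 84% power to detect differences of 0.47 standard deviations between walking with and without an AFO", at "a significance level of 0.02 to informally adjust for multiple testing". The analysis itself is to be a linear or generalised linear mixed model: "This approach will allow us to detect differences between walking with and without an AFO while adjusting for confounding variables". For that analysis, "The level of significance will be set at 0.05". The paragraph lists no model terms and does not name the confounders.

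**The concern.** The design and the analysis do not match. Order is randomised, and in the pilot the investigators balanced it because they thought a second test might be affected by fatigue. The analysis paragraph does not then say that order will be used. Its reference to confounders does not clearly cover order, because a factor split evenly by randomisation is not associated with condition.

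Balancing protects the mean difference and leaves its standard error unprotected. If the second test differs from the first by a constant shift, half the AFO-minus-no-AFO differences move up by that amount and half move down. A model with condition and patient only, which for complete data is the paired t-test, reads that split as random scatter. What is at stake is precision and power for initial walking distance, and an order effect that would go unreported.

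**Working it through.** **Inputs.** From the Aim 1 Statistical analysis paragraph: n = 50; effect 43.4 m and SD of the difference 93 m, given as 0.47 SD; level 0.02 for sizing and 0.05 for analysis; 1.29 SD for absolute distance. From the Approach paragraph: order split half and half, so 25/25. Sidedness is not stated, and I take two-sided. The order shift δ (second test minus first) is not in the documents. I take 20, 30 and 43.4 m, the last equal to the AFO effect itself.

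**Step 1: reproduce the plan's power.** Normal approximation: Φ(0.47 × √50 − 2.326) = Φ(3.323 − 2.326) = 84.1%, which matches the stated 84%. The exact noncentral t with 49 df gives 81.7%. I use the exact t below.

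**Step 2: what the shift does.** Write each paired difference as D = τ + δ + e if the AFO is tested second, and D = τ − δ + e if it is tested first, where e has SD σ. With 25 per order:
- The mean of D is τ, and its true variance is still σ²/50. There is no bias, and the shift adds no real variance to the mean.
- The ordinary sample variance S² has expectation σ² + δ² × 50/49, so the estimated standard error is inflated by about √(1 + (δ/σ)² × 50/49).
- 49S²/σ² follows a noncentral chi-square with 49 df and noncentrality 50(δ/σ)². Power without the term is the probability that |mean| exceeds t(49 df) × S/√50, averaged over that distribution.
- With an order term, the residual variance is σ² again and the error df are 48.

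**Step 3: cost of the term if δ = 0.** Power at 0.02 goes from 81.72% (49 df) to 81.67% (48 df).

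**Step 4: reading A, the 93 m SD excludes order variation** (σ = 93 m, d = 0.47).

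| δ | SE inflation | Power at 0.02 without / with term | Power at 0.05 without / with term | Type I error without term (nominal 0.02; 0.05) |
|---|---|---|---|---|
| 20 m | 2.3% | 80.2% / 81.7% | 89.4% / 90.3% | 0.0174; 0.0451 |
| 30 m | 5.2% | 78.3% / 81.7% | 88.4% / 90.3% | 0.0147; 0.0396 |
| 43.4 m | 10.6% | 74.4% / 81.7% | 86.1% / 90.3% | 0.0105; 0.0308 |

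Example for the inflation at 43.4 m: (43.4/93)² × 50/49 = 0.2222, and √1.2222 = 1.106.

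**Step 5: reading B, the 93 m SD already includes order variation.** Then σ = √(93² − δ²), which is 90.8, 88.0 and 82.3 m. The effect is held at 0.47 × 93 = 43.7 m. At level 0.02:

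| δ | Power without term | Power with term |
|---|---|---|
| 20 m | about 82% | about 84% |
| 30 m | about 83% | about 86% |
| 43.4 m | about 84% | about 91% |

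**Step 6: absolute distance.** At 1.29 SD the noncentrality is 1.29 × √50 = 9.12. Even with a shift of one full SD of the difference, power without the term exceeds 99.9% at 0.02.

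**The case against.** The strongest reply is that nothing here threatens the trial's validity. Order is balanced, the estimate is unbiased, and omitting the term makes the test conservative, so it cannot create a false positive. That stands.

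The text also does not rule the term out. It lists no terms at all, the investigators may use the word for confounders loosely, and order could be added at the analysis stage. That stands too. The point is that the term is not named, which leaves the choice open until the data have been seen.

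The fatigue remark belongs to a four-patient pilot, and the Aim 1 text does not repeat it. That is correct, but Aim 1 uses the same kind of treadmill test and again randomises order, so a shift is plausible. Its size is unknown. Against a pilot mean initial distance of 140.1 m without the AFO, shifts of 20, 30 and 43.4 m are 14%, 21% and 31%. Much larger shifts are hard to credit, and at 20 m or less the loss is small.

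A reader might infer that the study is underpowered relative to its stated 84%, or that the 84% is wrong. The documents support neither. The 84% reproduces with the normal approximation. The 93 m SD comes from a pilot that was itself counterbalanced two and two, so it may already contain order variation. In that case the paired analysis keeps its planned power, and the term is a gain over plan rather than the repair of a shortfall.

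**Conclusion.** The point holds as a free improvement. The Aim 1 analysis names no test-order term although order is randomised. If a shift between tests exists, the standard error is too large and power is lower than an order-adjusted model would achieve.

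For initial distance, with shifts of 20 to 43.4 m, the loss relative to the adjusted model at level 0.02 is about 1 to 7 points under either reading of the 93 m SD. At the analysis level of 0.05, with the SD taken to exclude order variation, it is about 1 to 4 points. Only under that reading of the SD does power fall below what the same exact calculation gives for the plan. Power for absolute distance is not materially affected.

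These figures assume two-sided tests, a constant additive shift, an even 25/25 split, complete pairs and a linear model. I am sure of the omission and of the direction of its effect. The size depends on a shift that the documents do not give.

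**What to change.** In the Aim 1 Statistical analysis paragraph, state that each mixed model includes fixed effects for condition (AFO, no AFO) and test order (first, second), with a random patient intercept. State that the order actually tested is recorded for every patient, since the documents do not say so, and that the order effect is reported with its confidence interval beside the AFO effect.

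The cost is one model term and one degree of freedom (81.72% to 81.67% power if there is no order effect). No extra patients, visits or measurements are needed.

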Specific Aim 1: Test the hypothesis that from its first use an AFO produces improvements in walking performance of patients with PAD by decreasing the required muscle contribution and energy cost of walking.

Specific Aim 2: Test the hypothesis that using an AFO for three months leads to progressive improvements in walking performance, physical activity levels and quality of life of patients with PAD and that these improvements correlate with improvements in the morphometric measurements, oxygenation levels, and muscle strength and endurance characteristics of the affected legs. We will use a crossover design, in which half of subjects will complete a three-month control period before, and half after, the AFO intervention.

Specific Aim 3: To determine the feasibility of a three month AFO intervention by examining acceptability (satisfaction, intent to continue use), demand (actual use, perceived demand), implementation (degree of use, success or failure of use, factors affecting use), and practicality (effects, ability of participants to use AFO).

If our hypothesis is correct, will be the first to demonstrate that a simple, accessible AFO device can rapidly improve functional status and quality of life in patients with PAD immediately by decreasing the required muscular contribution and oxygen demands to PAD muscle. Additionally, Aim #2 will evaluate the long-term effects of wearing an AFO on functional status and quality of life. Aim #3 will help the investigative team ensure it is feasible to implement the AFO in our target population. Detailed measures of mechanisms related with walking performance, muscle contribution, physical activity, quality of life and how these mechanisms change after wearing the AFO for three months will provide the evidence required to implement an AFO therapy that will improve functional status and quality of life in individuals with PAD.

2. Significance

Current treatments for PAD do not compensate for muscle myopathy

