AFO and Control Intervention: Patients will be asked to wear an AFO each day for three months. Subjects will have an off-the-shelf AFO (Figure 2) chosen initially based on shoe size and adjusted or exchanged for a different size during the initial evaluation after entering the study. The patients will be asked to wear the AFO at all times except when they are in bed or showering/bathing. The instructions given to the patients about walking will be the same as typically provided by clinicians, which is to walk 30 minutes per day, most days/week. We have chosen this specific AFO device because it is already available for use in a clinical environment, is composed of a carbon-composite material that will capture and return energy during the gait cycle, and has successfully contributed to propulsion during walking in other clinical populations^{26, 28}. Patients will be able to contact the nurse coordinator at any time if they need the AFO adjusted or have questions about what should happen during the intervention. Subjects in the control arm will be asked to continue the same lifestyle for three months. The intervention arm order will be randomized (see Statistical Analysis)

Outcomes: All outcomes will be assessed at baseline and following each arm (control and AFO).

- 1) Initial and absolute walking distances, 2) Lower extremity torque and power, 3) Muscle activity, and 4) Energy cost will all be measured as described for Specific Aim 1.
- 5) **Physical Activity:** Participants will wear the Actigraph (Actigraph GT3X, Actigraph, FL, USA) accelerometer on their hip for seven days (the whole day except when sleeping) prior to starting the AFO intervention to measure baseline activity level. The accelerometer will be mailed back to researchers in a pre-paid envelope. Two weeks prior to the post-intervention visit to the laboratory, an accelerometer will be mailed to participants to wear the final seven days before the visit. Average steps/day, maximum cadence, and average peak activity index will be calculated.

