- 6) **Quality of Life:** The Walking Impairment Questionnaire⁷⁴, Medical Outcomes Short Form 36, and Edinburgh Claudication Questionnaire will be used to assess quality of life. The Walking Impairment Questionnaire has been validated in patients with claudication⁷⁴ and the Short Form 36 has been extensively evaluated and tested with a variety of populations and is able to distinguish between groups of varying health status^{75, 76}. The Edinburgh Claudication Questionnaire was developed in an iterative, systematic fashion and has been implemented as a more holistic approach to identify presence of intermittent claudication in many clinical trials.^{20, 77-82}
- 7) **Morphometric parameters:** An ultrasound transducer (LS128 CEXT-1Z, Telemed, LT, Lithuania) will be used to assess thickness of the plantarflexor muscles using a standard real time B-mode image. Muscle thickness will be measured on the posterior medial and lateral surfaces, 20, 30, and 40% between the lateral malleolus of fibula and the lateral condyle of the tibia. The average values of muscle thickness at all measured sites will be the primary outcome measure.
- 8) **Muscle Oxygenation:** Continuous-wave near infrared spectroscopy (Moxy Monitor, Fortiori Design LLC, MN, USA) will be measured bilaterally on the gastrocnemius calf muscle before, during and after the walking distance test. We will measure resting StO₂, minimum StO₂ during the maximal treadmill test, time to minimum StO₂, and the StO₂ recovery time.
- 9) **Muscle Strength and Endurance:** An isokinetic dynamometer (Biodex 4 Medical Systems, Inc. USA) will be used to measure peak isokinetic strength (torque) of the ankle and hip of the more symptomatic leg. Peak torque and total work performed for ankle plantarflexion, ankle dorsiflexion, hip flexion, and hip extension will be measured. Subjects will perform one trial of five repetitions at 60 degrees/second to assess strength, and one trial of 15 repetitions at 120 degrees/second to assess endurance.

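### Ultrasound muscle thickness is read with no masking to visit or period in a crossover with a visible device; reading coded images in random order would cheaply reduce bias in the mean thickness change

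*Combined protocol and SAP*

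**What the plan says.** All of this is in the combined protocol and SAP, mostly in section 4, Approach, under Specific Aim 2.

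- **The measure.** Outcomes, item 7 (Morphometric parameters), has plantarflexor thickness assessed with an ultrasound transducer "using a standard real time B-mode image". Sites lie on the medial and lateral posterior surfaces at three levels of the lower leg, so six in all. The item ends: "The average values of muscle thickness at all measured sites will be the primary outcome measure".
- **When.** The Outcomes paragraph has every outcome assessed at baseline and again after each arm.
- **The two arms.** Under AFO and Control Intervention: "Patients will be asked to wear an AFO each day for three months". For the comparator: "Subjects in the control arm will be asked to continue the same lifestyle for three months". There is no sham device. The order of the arms is randomized.
- **What the measure is for.** Section 1, Specific Aim 2, hypothesizes gains in walking performance, activity and quality of life, and that "these improvements correlate with improvements in the morphometric measurements" and in other muscle characteristics.
- **What the team expects.** Expected results/possible limitations for Aim 2 anticipates that lower stress on the leg muscles will let them recover structurally and functionally.
- **Masking.** The document does not mention masking of a sonographer, reader, assessor or analyst. It does not say whether images are stored, coded or read in any particular order. Independent rating appears only for the Aim 3 interview transcripts.

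**The concern.** Thickness on an ultrasound image depends on where a person sets the measurement points. The patient knows which period has just ended, and nothing in the plan keeps that from the staff. If the reader knows it too, and shares the stated expectation that muscle improves with the AFO, readings after the AFO period could drift upward relative to those after control. Averaging over six sites reduces random reading error but leaves a shift common to all six intact.

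At stake is the mean thickness change that would be reported as a structural muscle gain. Treadmill walking with a visible device is hard to mask. The reading of a stored image can be masked without hiding the device from anyone.

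**Working it through.** **Inputs from the plan (Aim 2, Statistical analysis).** 30 patients, 15 per sequence; 80% power for 0.59 SD; paired t-test, used there for sample size estimation only; planning significance level 0.025; analysis level 0.05; 10% drop-out.

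**Input not in the plan.** The systematic reading shift b, in SDs of the within-patient AFO-minus-control difference in thickness. The documents give no thickness SD, reader error or expected change, so b is assumed over the range 0.1 to 0.3.

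**Step 1: reproduce the plan's own figure.** For a paired t-test with n patients and standardized difference d, the noncentrality is d × √n on n − 1 degrees of freedom. Here it is 0.59 × √30 = 0.59 × 5.477 = 3.23 on 29 df. The two-sided critical value at 0.025 is 2.364, and the power is 80.2%, which agrees with the stated 80%. (One-sided 0.025 would give 87.8%, so the plan evidently used a two-sided test.) Drop-out: 15 / 0.90 = 16.7, rounded up to 17 per group, 34 in total, as stated. These figures concern walking distance; the plan states none for thickness.

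**Step 2: false-positive rate for mean thickness.** Use the same formula with no true change and a reading shift b, so the noncentrality is b × √30. The two-sided critical value at 0.05 on 29 df is 2.045. An observed mean difference of 2.045 / 5.477 = 0.37 SD is therefore enough for significance.

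| Assumed shift b (SD) | Noncentrality | Rejection at 0.05 | Rejection at 0.025 |
|---|---|---|---|
| 0 | 0 | 5.0% | 2.5% |
| 0.1 | 0.55 | 8.3% | 4.6% |
| 0.2 | 1.10 | 18.5% | 11.7% |
| 0.3 | 1.64 | about 36% | about 25% |

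The plan's analysis is a mixed model; the paired test is a simplification, chosen because it is the plan's own planning test.

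**Step 3: the correlation with walking gain.** If every patient's thickness change T is read as T + b, the covariance of T + b with walking gain W equals the covariance of T with W, and the SD of T + b equals the SD of T. The Pearson correlation is unchanged, so the rates in Step 2 do not apply to it. A false correlation needs a shift that varies with the patient's walking result.

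One special case is pooling equal numbers of AFO-period and control-period changes, which the plan does not say it will do. With a walking effect of 0.59 SD and a reading shift of 0.3 SD (SDs of change within a period) and no true relation, the induced correlation is 0.25 × 0.59 × 0.3 / √[(1 + 0.25 × 0.59²)(1 + 0.25 × 0.3²)] = 0.044 / 1.054 = 0.04. That is negligible.

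**The case against.** The strongest reply has four parts.

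- **The text does not establish unmasked live reading.** Real-time B-mode names an imaging mode. The plan does not say whether measurement points are set during the scan or on stored frames, or who sets them. This stands: that the reader knows the period is an inference from a visible device, no sham and no masking rule, and the document never calls the study open. But masking is specified for neither way of reading, so the gap remains.
- **The shift is assumed.** This also stands. The table shows how sensitive a test of mean thickness would be to a shift, not that one will occur.
- **Thickness matters little to the main result.** It is primary only within item 7. The main Aim 2 comparison is walking distance, and the plan says the AFO would still be useful if walking, activity and quality of life improved without better muscle function. This limits the importance of the point.
- **Coding images is only a partial remedy.** Probe position, probe pressure and choice of frame are settled at the visit, where the operator may know the period. This stands, so the fix reduces the bias and does not prevent it.

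A reader might also infer that a biased reading would produce the very correlation Aim 2 is looking for. The documents do not support that. A constant shift leaves the correlation unchanged, and nothing in the plan shows that a shift would follow each patient's walking result. Walking is assessed at the same time points and nothing separates the staff, so it is possible, but no more than that.

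Nor does the point extend to the gait and EMG measures: the plan describes software calculation for them and mentions no manual reading step.

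**Conclusion.** The point holds as a modest one. An operator-dependent measure is taken after each arm of a crossover in which the device is visible and there is no sham. The team has a stated expectation about the direction of change, and no masking of the reading is specified. If a reader's knowledge of the period shifted the mean difference by 0.1 to 0.3 SD, the chance of a false mean thickness gain at two-sided 0.05 with 30 patients would rise from 5% to between about 8% and 36%.

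This rests on the assumed shift, on no true change, on 30 patients with all readings, and on a paired test standing in for the mixed model. It concerns the mean thickness change only. The walking-distance comparison, the sample size and the power are unaffected.

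**What to change.** In Aim 2, Outcomes, item 7, add that the ultrasound images will be saved; that patient, visit and period labels will be replaced with codes before measurement; and that whoever would otherwise measure them will read each patient's images in one batch, in random order, after that patient's last visit.

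State alongside it that this masks the reading step only, and that probe position, probe pressure and frame choice remain open to influence if the operator knows the period.

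The cost is a relabelling step, slightly more data handling and later availability of the thickness values. It needs no extra reader, visit, procedure or patient. Label: cheap improvement.
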